19.3 Confidentiality

All personal details of the participating subjects and the results of the trial will be kept strictly confidential. Each subject's GP (or equivalent physician) will be informed of the nature and timing of the trial.

All unpublished documents including the protocol, the CRF, and the IB are confidential. Those documents cannot be disclosed to a third party without the written consent of the sponsor. However, submission of those documents to a REC is expressly permitted.

The investigator agrees that the sponsor maintains the right to use the results of this trial, in their original form and/or in a global report, for submission to governmental and regulatory authorities of any country.

19.4 Publication

If the data merit, the investigator and the sponsor will discuss the preparation of a manuscript for publication in a peer-reviewed professional journal or an abstract for presentation, oral or written, to a learned society or symposium. Either party may undertake the task but both must agree to the strategy before the work is started.

Each party will allow the other 30 days to comment before any results are submitted for publication or presentation. Authorship should reflect work done by the investigators and personnel of the sponsor, in accordance with generally recognised principles of scientific collaboration.

19.5 Archiving

The sponsor and HMR will keep in a trial master file all the essential documents required by GCP. HMR will ensure that the investigator's master file, and all data generated during the trial, will be archived in a secure place for at least 25 years. Documents will be stored such that they are readily available for inspection at the request of the sponsor or a regulatory authority. Any transfer of ownership of the investigator's data or documents will be documented, and the sponsor will be informed.

20 Premature termination of the trial

The sponsor and investigator reserve the right to terminate this trial should severe AEs, SAEs or any other safety issue occur during the trial. If the trial is terminated prematurely, and the sponsor or investigator, as appropriate, will provide a written statement of the reasons for termination. The sponsor will ensure that the MHRA and REC are notified, as described in section 17.

21 References

1. World Health Organisation. <https://www.who.int/news-room/fact-sheets/detail/dementia>

### Version control history

Version	Reason for change
1, dated 22 May 2023	N/A
1.1, dated 12 Jun 2023	Updated a formatting error in section 12.1 in relation to Appendix A and Appendix B. Removed column “Study Day” from T14.2.1.1 as not required.

## 1 List of abbreviations

$\lambda_z$	Terminal rate constant
AE	Adverse event
ANOVA	Analyses of variance
ANCOVA	Analysis of covariance
AUC	Area under concentration-time curve
AUC inf	AUC from time zero to infinity
AUC tau	AUC for the dosing interval
AUC last	AUC from time zero to last measurable concentration
%AUC extrap	Percentage of AUC inf extrapolated from tlast to infinity
BMI	Body mass index
BQL	Below the limit of quantification
CI	Confidence interval
CL ss /F	Apparent total body clearance at steady state
C max	Maximum plasma concentration
C trough	Trough concentration
CRF	Case report form
CSR	Clinical study report
C-SSRS	Columbia-Suicide Severity Rating Scale
CV	Coefficient of variation
CV b	Between-subject CV
ECG	Electrocardiogram
FDA	Food and Drug Administration
HR	Heart rate
ICH	International Conference on Harmonization
IV	Intravenous
LSM	Least Square Means
MedDRA	Medical Dictionary for Regulatory Activities
N	Number of subjects
n	Number of observations used in analysis
PBMC	Peripheral blood mononuclear cell
PET	Positron emission tomography
PD	Pharmacodynamic
PK	Pharmacokinetic(s)
PR	Portion of the ECG from the beginning of the P wave to the beginning of the QRS complex, representing atrioventricular node function.
QD	Once a day
QRS	The QRS complex of the ECG reflects the rapid depolarization of the right and left ventricles
QT	Portion of the ECG between the onset of the Q wave and the end of the T wave, representing the total time for ventricular depolarization and repolarization.
QTc	Corrected portion of the ECG between the onset of the Q wave and the end of the T wave, representing the total time for ventricular depolarization and repolarization
QTcF	QTc interval with Fridericia's correction method
R ac(AUC)	Accumulation ratio for AUC
R ac(Cmax)	Accumulation ratio for Cmax
RO	Receptor Occupancy

RR	Portion of the ECG between consecutive R waves, representing the ventricular rate
SAE	Serious adverse event
SAP	Statistical analysis plan
SD	Standard deviation
SRG	Safety Review Group
$t_{1/2}$	Terminal elimination half-life
TEAE	Treatment-emergent adverse event
$t_{max}$	Time to maximum plasma concentration
$V_z/F$	Apparent volume of distribution
$V_T$	Volume of distribution
WHO	World Health Organisation

### **3 Introduction**

This statistical analysis plan (SAP) is based on the current trial protocol (version 2, 23 January 2023). Where statistical methods differ substantially between this SAP and the protocol, that will be identified in this document.

This SAP describes the datasets and the statistical methods to be used for the reporting and analysis of all data collected during the trial except the PET data analysis which will be analysed and reported separately by Invicro.

If a future protocol amendment necessitates a substantial change to the statistical analysis of the trial data, this SAP will be amended accordingly. If, after database lock, additional analyses are required to supplement the planned analyses described in this SAP, those unplanned analyses will not be described in an amended SAP, but they will be identified in the integrated clinical study report (CSR). Any deviations from this SAP will be documented in the CSR.

This SAP has been written in consideration of the following guidelines:

- International Conference on Harmonization (ICH) E9, Guidance for Industry: Statistical Principles for Clinical Trials (ICH E9 1998); and
- ICH E3, Guidance for Industry: Structure and Content of Clinical Study Reports (ICH E3 1995).

Pharmacokinetic (PK) analysis will be done using WinNonlin v8.1 or higher on a Windows PC. Statistical analysis will be done using SAS® 9.4 or higher on a Windows PC.

### **4 Study objective(s) and endpoint(s)**

#### **4.1 Study objective(s)**

##### **4.1.1 Primary objective(s)**

- To assess the pharmacodynamic (PD) response in peripheral blood mononuclear cells (PBMCs) following single and repeated oral doses of ASN51 in healthy subjects.
- To assess brain O-GlcNAcase occupancy using [F]-IMA601 positron emission tomography (PET), following repeated oral doses of ASN51 in healthy subjects.

##### **4.1.2 Secondary objective(s)**

- To assess the safety and tolerability of repeated oral doses of ASN51 in healthy subjects
- To assess the relationship between the plasma concentration of ASN51 and the time-course of brain O-GlcNAcase occupancy using [F]-IMA601 PET, following repeated oral doses of ASN51 in healthy subjects

- To assess the pharmacokinetics (PK) of repeated doses of ASN51 in healthy subjects
- To assess the trough O-GlcNAcase occupancy of ASN51 after repeated doses in healthy subjects
- To determine the effect of food on the PD response in PBMCs following repeated ASN51 dosing in healthy subjects

## 4.2 Study endpoint(s)

### 4.2.1 Primary endpoint(s)

#### PD:

- Protein O-GlcNAcylation in PBMCs
- $[^{18}\text{F}]\text{-IMA601}$  regional total volume of distribution ( $V_T$ ) at each brain scan

### 4.2.2 Secondary endpoint(s)

#### Safety and tolerability:

- vital signs (blood pressure, pulse rate, tympanic temperature, and respiratory rate), 12-lead safety electrocardiogram (ECG), physical and neurological examination, laboratory safety tests (haematology, clinical chemistry, coagulation, and urinalysis), Columbia-Suicide Severity Rating Scale (C-SSRS), and adverse events (AEs)

#### PK:

- plasma concentration of ASN51 at the time of each postdose PET scan
- PK parameters including  $C_{\text{max}}$ ,  $C_{\text{max}}/\text{Dose}$ ,  $t_{\text{max}}$ ,  $t_{1/2}$ ,  $\lambda_Z$ ,  $AUC_{\text{tau}}$ ,  $AUC_{\text{last}}$ ,  $AUC_{\text{inf}}$ ,  $AUC_{\text{inf}}/\text{Dose}$ ,  $\%AUC_{\text{extrap}}$ ,  $CL_{\text{SS}}/\text{F}$ ,  $V_Z/\text{F}$ ,  $C_{\text{trough}}$ ,  $R_{\text{ac}}(C_{\text{max}})$ ,  $R_{\text{ac}}(AUC)$ .

#### PD:

- Protein O-GlcNAcylation in PBMCs with or without prior feeding
- Trough  $[^{18}\text{F}]\text{-IMA601}$   $V_T$

#### PK/PD:

- relationship between ASN51 plasma concentration, PBMC target engagement, and brain receptor occupancy (RO) over time

## 4.3 Statistical hypotheses

The trial is an exploratory one, and there are no null hypotheses to be tested.

## 5 Study design

This is a phase 1, open-label, dose escalation, PET study to investigate the brain occupancy of O-GlcNAcase, and the PD response in PBMCs, after repeated doses of ASN51 in healthy subjects.

Enrolment of up to 12 healthy subjects is planned, in up to 2 groups (Groups 1 and 2). Each group will consist of up to 6 subjects.

All subjects will receive once-daily (QD) doses of ASN51, by mouth, for 14 days: Group 1 will receive [REDACTED] ASN51 QD and Group 2 will receive [REDACTED] ASN51 QD. Group 2 will proceed only if the safety and tolerability of the previous dose level are acceptable, and the plasma concentrations of ASN51 are predicted to remain below the toxicokinetic limit, as determined by the Safety Review Group (SRG; see protocol section 8.5).

On Day 11, to evaluate the effect of food on PBMC response, subjects will receive ASN51 in the fed state following a United States Food and Drug Administration (FDA) high-fat breakfast. Subject fasting requirements are further detailed in protocol section 11.

In each group, 2 subjects will have a PBMC-only study design (section 5.1.1) and 4 will have a PBMC and PET scanning study design (section 5.1.2).

Schematic diagrams of each study design are in protocol section 8.2.

### 5.1.1 PBMC-only subjects

2 subjects in each of Groups 1 and 2 will not have PET scans during the study. They will:

- be screened within 28 days before their first dose of trial medication.
- be resident on ward from 1 day before their first dose (Day -1) until 6 days after their final dose (Day 20).
- return for a follow-up visit 9–11 days after their final dose of trial medication (Days 23–25).

### 5.1.2 PET subjects

4 subjects in each of Groups 1 and 2 will have PET scans during the study. PET subjects will:

- be screened within 21 days before imaging session 1 (see below).
- be resident on ward from 1 day before their first dose (Day -1) until 6 days after their final dose (Day 20); and have imaging sessions as described below.
- return for a follow-up visit 9–11 days after their final dose of trial medication (Day 23 ± 2 days), or 2–4 days after imaging session 3 (see below), whichever is later.

PET subjects will have up to 3 imaging sessions, as follows.

- *Imaging session 1.* Subjects will have a baseline PET scan between Day –7 and Day –3. Subjects will be admitted to the ward the day before their baseline PET scan, and be discharged the following day after their scan.
- *Imaging session 2.* Subjects will have an on-treatment PET scan at about 5 h postdose on Day 1.
- *Imaging session 3.* Subjects will have an on-treatment PET scan at 3–9 days after their final dose of ASN51:
  - 3 subjects per group on Day 17
  - 1 subject on Day 22 ( $\pm$  1 day) (Group 1 only)
  - 1 subject on Day 23 ( $\pm$  1 day) (Group 2 only)

The timing of on-treatment PET scans (imaging sessions 2 and 3) may be altered based on emerging data or study logistical requirements.

Subjects will receive an intravenous (IV) dose of the radiolabelled tracer, [F]-IMA601, at the start of each PET scan.

Arterial blood sampling will be done during each PET scan to quantify the parent tracer-related radioactivity over the course of the PET scan, and to establish a tracer metabolite-corrected plasma input function. The total arterial blood volume required for each tracer injection will not exceed 120 mL. Arterial cannulation and arterial blood sampling may be reduced or removed if analysis of PET data from previous subjects indicates that non-invasive analysis of the PET scan data can be done. If a non-invasive analysis is not possible, the use of an arterial cannula with each PET scan will continue through the study.

In the case of a technical failure (such as unsuccessful tracer synthesis), subjects may be asked to attend an additional on-treatment imaging session as described in section 12.2 of the protocol. However, no subject will have more than 3 PET scans and 3 doses of [F]-IMA601 during the study. See section 8.2 of the protocol for the design flow charts.

## 6 Time and events table

Please refer to section 12.1 of the protocol, version 2, dated 23 January 2023 and file note Ward 2.

## 7 Planned analyses

No interim analyses are planned. However, data will be reviewed for dose selection.

## 7.1 Interim analyses

No interim analyses are planned. However, safety and pharmacokinetic data from Group 1 will be reviewed before proceeding to Group 2.

## 7.2 Final analysis

The database will be locked once all subjects have completed the study, data have been entered, and queries resolved. The final analysis will be carried out following database lock.

### 7.2.1 Persons responsible for analysis

## Statistician

## 8 Sample size considerations

## 8.1 Sample size assumptions

Since this trial is hypothesis generating, no formal calculation of sample size is appropriate.

The sample size chosen is considered adequate to allow modelling of the relationship between ASN51 plasma concentrations and pharmacodynamic target engagement using an exploratory PBMC protein O-GlcNAcylation assay.

PET analyses of 8 subjects is sufficient to define the occupancy of O-GlcNAcase and is within the range generally accepted for PET studies.

## 9 Analysis populations

The following populations will be identified:

Safety population: All subjects who received at least one dose of study drug

PET population: All subjects in the safety population who had a baseline PET scan, at least 1 post-baseline PET scan, and a PK result immediately preceding a PET scan

PD analysis population: All subjects in the safety population for who a PBMC measure is available.

PK analysis population: The PK analysis population will consist of the subjects who provide evaluable data for the comparisons of interest. These subjects should have at least one quantifiable plasma concentration, should not have violated any major entry criterion likely to confound the PK analysis, and should not have deviated significantly from the protocol between enrolment and successful study completion

The primary endpoints will be analysed using the PET and PD populations. The secondary endpoints will be analysed using the Safety, PET and PD populations.

## 9.1 Analysis datasets

All analysis datasets will be based on observed data, except as outlined in Section 12.2.

## 10 Treatment comparisons

The treatment comparison of interest is study drug between ascending doses.

## 11 General considerations for data analyses

### 11.1 Data display treatment and other subgroup descriptors

The sort order for treatment groups will be study treatment in ascending dose order.

Listings of data will be sorted and displayed by treatment group, subject number, and also by date and time if applicable.

The treatment descriptions to be used on all tables and listings are:

Treatment Groups
██████████ ASN51 (QD for 14 Days)
██████████ ASN51 (QD for 14 Days)

### 11.2 Conventions for summary statistics and data displays

The minimum set of summary statistics for numeric variables will be: n, mean, standard deviation, median, minimum, and maximum. 95% confidence intervals (CI) will be presented where appropriate for data interpretation.

Categorical data will be summarised in frequency tables with n and percentage. Summaries of a categorical variable will include all recorded values.

The minimum and maximum values will be presented with the same number of decimal places as the raw data collected on the CRF (or to 3 significant figures for derived parameters less than 100 and as integers for values more than 99). The mean and percentiles (eg median) will be presented using one additional decimal place. The standard deviation and standard error will be presented using two additional decimal places.

## 12 Data handling conventions

### 12.1 Premature withdrawal and missing data

All subjects who withdraw prematurely from the study or study drug will be included in the statistical analyses.

If a subject completes the treatment period but has missing data, then this will be made apparent in the subject listings. Missing data will not be imputed except for as outlined in Section 12.2.

If the study is prematurely discontinued, all available data will be listed and a review will be carried out to assess which statistical analyses are still considered appropriate.

Data collected at unscheduled time points during the study will not be used in the summaries or data analyses. They will be included in the listings.

If time information (ie hours and/or minutes) for adverse events (AEs) or concomitant medication is missing, but the day is present, then the time will be calculated in days. If date information is partial or missing, then any derived times (eg AE start time from last study medication) will be listed as missing.

Conventions for handling missing plasma concentrations are given in Appendix B: Pharmacokinetic analysis

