24. Clinically significant ECG abnormalities, as determined by the investigator or medical monitor, including (but not limited to):
 - abnormal ST-T-wave morphology or left ventricular hypertrophy.
 - PR (PQ) interval shortening < 120 msec (PR < 120 msec but > 110 msec is acceptable if there is no evidence of ventricular pre-excitation).
 - PR (PQ) interval prolongation (> 220 msec), intermittent second- (Wenckebach block while asleep or in deep rest is not exclusionary) or third-degree atrioventricular (AV) block.
 - Persistent or intermittent complete bundle branch block, incomplete bundle branch block, or intraventricular conduction delay with QRS > 120 msec.
25. Blood pressure and pulse rate in seated position at the screening examination outside the ranges: blood pressure 90–140 mm Hg systolic, 40–90 mm Hg diastolic; pulse rate 40–100 beats/min. The average of triplicate measurements (each 5 min apart) will be used to assess eligibility.
Repeat measurements are permitted if values are borderline (ie values that are within 5 mm Hg for blood pressure or 5 beats/min for pulse rate) or if requested by the investigator. Subjects can be included if the repeat value is within range or still borderline, but deemed not clinically significant by the investigator.
26. Significant ($> 10\%$) weight loss or gain within 30 days before the (first) screening visit or before the baseline PET scan (PET subjects) or first dose of trial medication (PBMC subjects).
27. Unsatisfactory venous access
28. Subjects with a COVID-19 vaccination within 2 weeks of screening, or who are due to receive a dose of a COVID-19 vaccine while participating in the study.

29. Positive test for hepatitis B, hepatitis C or human immunodeficiency virus (HIV).
30. Vegan, or unwilling to eat a high-fat breakfast including eggs and dairy (eg for personal or religious reasons).
31. Employed by, or a first-degree relative of an employee of, Asceneuron S.A. or a clinical trial site participating in this study.
32. Possibility that the volunteer will not cooperate with the requirements of the protocol.
33. Objection by general practitioner (GP) to volunteer entering trial.

The following exclusion criteria also apply to subjects who will be given PET scans during the study.

34. Significant structural brain abnormality, as determined by MRI.

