13. Full physical and neurological examinations will be done at screening and at the follow-up visit. Brief (symptom-directed) physical examinations will be done at all other timepoints.
14. FSH tests in post-menopausal women (screening only).
15. Weight only at screening visit 2 (MRI; PET subjects only).
16. Vital signs consist of seated systolic and diastolic blood pressure, pulse rate, tympanic temperature, and respiratory rate. Vital signs will be done at the following timepoints.
 - *PBMC-only subjects*: screening; Day -1; predose and at 2, 4, 8, and 12 h postdose on Day 1; before dosing on Days 2–13; before, and at 2, 4, 8, and 12 h after dosing on Day 14; at 24 h (Day 15), 48 h (Day 16), 72 h (Day 17), 96 h (Day 18), 120 h (Day 19), and 144 h (Day 20) after the last dose of ASN51; and at follow-up
 - *PET subjects* will have the same timepoints as PBMC-only subjects, plus additional assessments at: imaging session 1 (baseline) and imaging session 3 (if held on Day 22 or Day 23)TriPLICATE measurements (obtained \geq 5 min apart) will be made at screening. Single measurements will be made at all other timepoints. Measurements should begin with subjects in a seated position, after resting for at least 5 min. Additional unscheduled assessments may be done at the discretion of the investigator. Morning vital signs should always be taken before study drug administration.
17. During the period of residence, ECGs will be recorded at the following timepoints.
 - *PBMC-only subjects*: screening; Day -1; predose and at 2, 4, 8, and 12 h postdose on Day 1; before dosing on Days 2–13; before, and at 2, 4, 8, and 12 h after dosing on Day 14; at 24 h (Day 15), 48 h (Day 16), 72 h (Day 17), 96 h (Day 18), 120 h (Day 19), and 144 h (Day 20) after the last dose of ASN51; and at follow-up
 - *PET subjects* will have the same timepoints as PBMC-only subjects, plus additional assessments at: imaging session 1 (baseline) and imaging session 3 (if held on Day 22 or Day 23)TriPLICATE recordings (obtained \geq 5 min apart) will be made at screening. Single recordings will be done at all other time points. Recordings should be made with subjects in a supine position, after resting for 5 min.

18. Laboratory safety tests consist of haematology, clinical chemistry, coagulation, and urinalysis. Samples are to be taken at screening, Day -1, before dosing on Days 8 and 14, on Day 20, and at follow-up. Samples for clinical chemistry only are to be taken at Imaging session 1.

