## **12.2 Derived and transformed data**

Baseline will be considered to be the latest value obtained before study drug administration (eg Day 1, pre-dose; or Day –1 if not recorded at pre-dose; or screening if not recorded at pre-dose or on Day –1).

Laboratory data will be reported in standard units. Out-of-range laboratory tests may be repeated. If a test is out of-range at baseline and repeated before dosing, the latest repeat value before dosing will be used as baseline. However, if a test is out-of-range and repeated at any other time during the study, the out-of-range value (not the repeat value) will be included in statistical summaries.

TriPLICATE ECG and vital sign measurements will be made at screening and the mean of the three measurements for each subject will be used for analysis.

TriPLICATE PBMC measurements will be made and the mean of the three measurements for each subject will be used for analysis.

The PK parameters to be derived are given in Appendix B: Pharmacokinetic analysis.

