#### **14.6.2 ECG**

QT interval data will be presented using Fridericia's (QTcF) corrections.

ECG variables will be summarised by treatment and time point. Differences from baseline (Day 1 pre-dose) will be summarised by treatment and time point.

QTcF values > 450 msec, PR interval shortening < 110 msec, and PR interval prolongation > 220 msec, and increases of QTcF from baseline of > 30 msec and > 60 msec, will be listed by treatment and timepoint and summarised. A separate listing of ECG findings classified as abnormal by the investigator will also be provided.

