### Template T\_LB3

Table 14.3.4.xx Summary of laboratory values outside the reference range by treatment

Laboratory Test (units)	Treatment	m	H	L	Overall*
	Treatment 1 (N=xx)				

Source: Listing 16.2.xx

H = Above reference interval, L = Below reference interval

Subjects only counted once per treatment per category

\*Subjects only counted once per treatment

*m = total number of results for that parameter*

*Programming notes: Continued with all tests, treatment groups and time points. The summary is based on the reference ranges (most common ranges used)*

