**Template T\_EG3**

Table 14.3.7.xx Summary of QTcF and PR interval values outside the normal range by treatment, planned relative time and category

Treatment	Time	QTcF (msec)				PR int. (msec)			
		Planned		>30-60		>60		<120	
		Relative	451 – 480	481 – 500	> 500	Increase	Increase	<120	>220
Treatment 1 (N=xx)	Time 1								
	Time 2								

Source: Listing 16.2.xx

Programming notes: *Continued with all treatments and time points. n = total number of results for that parameter*

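### Shell T_EG3 counts PR below 120 msec as out of range where the SAP and protocol text say below 110 msec; separately, barring unscheduled values could understate the once-per-subject safety counts

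*SAP*

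**What the plan says.** **PR limit.** SAP 14.6.2 names the ECG values to be both listed and summarised, among them "PR interval shortening < 110 msec" and prolongation above 220 msec. Protocol 16.2.6.3 gives the same two limits, and protocol Table 6 gives a PR range of 110–220 msec. The shell for Table 14.3.7.2, T_EG3, is titled "Summary of QTcF and PR interval values outside the normal range by treatment, planned relative time and category". Its PR columns are < 120 and > 220 msec. At entry, protocol exclusion criterion 24 names shortening below 120 msec, then adds that "PR < 120 msec but > 110 msec is acceptable" when there is no evidence of ventricular pre-excitation.

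**Unscheduled values.** SAP 12.1 states: "Data collected at unscheduled time points during the study will not be used in the summaries or data analyses". The next sentence adds: "They will be included in the listings". SAP 12.2 deals with repeated laboratory tests. A repeat made before dosing becomes the baseline; for a test repeated at any other time, "the out-of-range value (not the repeat value) will be included in statistical summaries". The protocol foresees extra checks. The vital-signs note in section 12.1 says: "Additional unscheduled assessments may be done at the discretion of the investigator".

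Three shells count each subject once rather than by visit: T_LB3 ("Summary of laboratory values outside the reference range by treatment"), T_VS3 (vital signs) and T_EG4 (QTcF and PR). T_VS3 and T_EG4 are restricted to post-treatment time points; T_LB3 states no such restriction.

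**The concern.** The PR column of T_EG3 contradicts the text that defines the analysis. A value of 110–119 msec is in range under SAP 14.6.2 and protocol Table 6, and out of range in the table. Criterion 24 allows people with such values into the trial, so the gap can matter in practice. Table 14.3.7.2 cites Listing 16.2.9.3 as its source. If that listing follows the text, the table will report values that its own source does not contain.

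The rule on unscheduled values suits means by visit, where an extra observation has no planned time to belong to. It suits less well a table that asks whether a subject was ever out of range. If a subject's only abnormal value, or the worst one, comes from an unscheduled check, that subject is left out of the count or placed in too mild a category. T_EG4 grades QTcF as 451–480, 481–500 and > 500 msec, so the worst value matters there.

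Safety and tolerability is a secondary objective, and with up to 6 subjects per group each count carries weight.

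**Working it through.** The plan states no figure to reproduce on this point. The check sets the passages side by side, counts the ECGs, and then illustrates the size on stated assumptions.

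**1. PR limits side by side**

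| Place | Low PR limit | High PR limit |
|---|---|---|
| SAP 14.6.2 | < 110 msec | > 220 msec |
| Protocol 16.2.6.3 | < 110 msec | > 220 msec |
| Protocol Table 6 (range) | 110 msec | 220 msec |
| SAP shell T_EG3 | < 120 msec | > 220 msec |
| SAP shell T_EG4 | not legible here | not legible here |

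The high limit agrees wherever it can be read; only the low limit differs. SAP section 3 promises to identify substantial differences from the protocol, and SAP section 17 lists only updates to time points. SAP 19.1 gives a precedence rule for table numbering but none for table content. A programmer therefore has no rule for choosing between 110 and 120. The sample row in listing shell L_EG1 flags a PR of 109 msec, which fits either limit.

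**2. Scheduled post-dose ECGs per subject** (protocol 12.1, ECG note)

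- Day 1, at 2, 4, 8 and 12 h: 4
- Days 2–13, before dosing: 12
- Day 14, before dosing and at 2, 4, 8 and 12 h: 5
- Days 15–20: 6
- Follow-up: 1

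Total: 4 + 12 + 5 + 6 + 1 = 28. The one PET subject per group scanned on Day 22 or 23 has an additional ECG at that session: 29. Over 12 subjects: 12 × 28 + 2 = 338.

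A subject with a stable PR between 110 and 120 msec is flagged at all 28 (or 29) under < 120 and at none under < 110.

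**3. Share of values affected (illustration).** The documents give no PR distribution. Assume a normal distribution in whole msec, so that the cut-offs are 109.5 and 119.5, and ignore the effect of entry screening. At mean 150, SD 20:

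- P(PR < 110) = Φ((109.5 − 150)/20) = Φ(−2.025) = 2.1%, or about 7 of 338 values
- P(PR < 120) = Φ((119.5 − 150)/20) = Φ(−1.525) = 6.4%, or about 21 of 338 values

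Over means of 140–160 and SDs of 15–25 msec, the share flagged runs from 0.04% to 11.1% at < 110 and from 0.35% to 20.6% at < 120. The shell flags about 1.9 to 9 times as many values as the text.

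**4. Unscheduled values.** A once-per-subject count changes only if the subject's sole abnormal value was unscheduled, or the unscheduled value falls in a worse category. One subject is 1/6 = 16.7 points of a group of 6, or 1/12 = 8.3 points of 12. The documents give no rate for this, so let q be the assumed share of subjects whose only abnormal value is unscheduled. The chance of missing at least one of 12 is 1 − (1 − q)^12:

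- q = 2%: 21.5%
- q = 5%: 46.0%
- q = 10%: 71.8%
- q = 20%: 93.1%

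Laboratory tests are the most thinly scheduled: after the first dose they fall only on Days 8, 14 and 20 and at follow-up.

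**The case against.** **On PR.** The 120 msec figure has a visible source, since criterion 24 itself uses it before granting the exception. That explains how it may have reached the shell. It does not reconcile the shell with SAP 14.6.2, which governs both the listing and the summary. A reader might infer that both ECG shells carry the wrong limit. Only T_EG3 can be confirmed, because the PR header of T_EG4 did not survive the reading of the PDF.

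**On unscheduled values.** The case for the rule is substantial, and most of it stands.

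- The values are kept in the listings, and out-of-range listings are planned for laboratory tests, vital signs and ECGs.
- When an out-of-range laboratory test is repeated after baseline, the out-of-range value stays in the summaries. A repeat vital sign or ECG ordered because a scheduled value was out of range adds nothing to a once-per-subject count.
- Under protocol 14.2 an abnormal result that brings symptoms, concern or intervention is reported as an adverse event, and the adverse event tables are not built on scheduled time points.
- Counting scheduled values only gives subjects a similar number of chances to be flagged, which suits a comparison between dose groups.
- The protocol allows unscheduled checks at the investigator's discretion. That they are prompted by a symptom is plausible, but it is not stated.

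What remains is the case that none of these covers: a first or worst abnormal value at an unscheduled check that is not reported as an adverse event. The laboratory repeat rule does not reach a first abnormal result at an unscheduled draw, nor any unscheduled ECG or vital sign.

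**Conclusion.** The PR contradiction holds and should be corrected before the tables are programmed. As the shell stands, Table 14.3.7.2 would count values of 110–119 msec that the SAP and protocol text treat as in range: up to 28 or 29 ECGs for one eligible subject with a stable PR in that band. The ECG count rests on the protocol 12.1 schedule; SAP sections 6 and 17 refer to a file note with updated time points that is not in these documents. The mismatch with Listing 16.2.9.3 arises only if the listing follows the text.

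The point on unscheduled values is secondary: a possible understatement of T_LB3, T_VS3 and T_EG4, whose size depends on a rate that the documents do not give. A reader might go further and infer that the out-of-range counts would be wrong, that unscheduled data enter no summary at all, or that a transient laboratory rise between visits would appear in no table. The documents do not support this. The effect needs a subject whose only or worst abnormal value was unscheduled; a pre-dose laboratory repeat does enter the summaries as baseline; and an important abnormality can reach the adverse event tables.

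No primary endpoint is touched. The decision to open Group 2 does not depend on these tables, because the Safety Review Group reviews the safety data directly (protocol 8.5.1).

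**What to change.** 1. In shell T_EG3, change the low PR column from < 120 to < 110 msec, to agree with SAP 14.6.2, protocol 16.2.6.3 and protocol Table 6. Check the PR columns of T_EG4 against the same limit, and confirm that Listing 16.2.9.3 uses it. If < 120 msec was intended, say so in SAP section 17 and change the text and listing to match. The cost is one column header, perhaps two, and no new data.

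2. Consider limiting the exclusion in SAP 12.1 to by-timepoint summaries and analyses, and stating that unscheduled post-dose values count in T_LB3, T_VS3 and T_EG4. The cost is one sentence. The drawback is that subjects who are checked more often have more chances to be counted, which could blur the comparison between doses. If the sponsor prefers the present rule, a footnote on those three tables saying that they cover scheduled values only, with a pointer to the listings, would tell the reader what the counts leave out.
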